# 7.2.2.2 Hypothesis

The hypotheses to be evaluated in the analysis of the ORR are as follows:

 $H_0$ :  $ORR_{Cabozantinib} \leq ORR_{Placebo}$ 

 $H_A$ :  $ORR_{Cabozantinib} > ORR_{Placebo}$ 

where ORRCabozantinib and ORRPlacebo are the ORRs for the cabozantinib and placebo arms, respectively.

### 7.2.2.3 Primary Analysis

Hypothesis testing for ORR will be performed using the Fisher's exact test at the 2-sided  $\alpha$ =0.01 level of significance. If a sufficient number of responders are observed, analysis using the Cochran-Mantel-Haenszel (CMH) method to adjust for stratification factors per IxRS may also be conducted. The testing of ORR will occur only if the result of either an interim analysis or the final analysis of OS achieves statistical significance. The primary analysis of ORR will include all subjects in the ITT population.

Point estimates of ORR for each treatment arm, the difference in ORR between the two treatment arms, and associated confidence intervals will be provided. The odds ratio and its confidence intervals will also be shown. The 95% CIs for the point estimate will be calculated using exact methods. The 95% CIs for the difference in ORR between the two treatment arms and for the odds ratio will be calculated by asymptotic methods.

If the p-value for the two-sided Fisher's exact test is less than 0.01 and the point estimate for ORR in the cabozantinib arm is higher than that in the placebo arm, the null hypothesis of no difference in ORR will be rejected and it will be inferred that ORR is superior in the cabozantinib arm compared with the placebo arm.

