### **9.3.2 Objective Response Rate (ORR)**

The ORR is defined as the proportion of subjects experiencing a confirmed complete response (CR) or confirmed partial response (PR) per RECIST 1.1. The tumor response will be assessed by investigator.

Hypothesis testing will be performed using the Fisher's exact test at the 2-sided  $\alpha=0.01$  level of significance.

Point estimates of ORR, the difference in ORR between the two treatment arms, and associated confidence intervals will be provided. 95% CIs will be calculated using exact methods except for the difference in ORR between the two treatment arms which will use asymptotic confidence limits.

If sufficient responses are observed, additional supportive analyses will be conducted using appropriate methods to adjust for stratification factors.

The primary analysis of ORR will be performed for those subjects who have measurable disease at baseline within the ITT population. Subjects who do not have any post-randomization tumor assessments will be counted as non-responders.

The testing of ORR will occur only if the result of either an interim analysis or the final analysis of OS achieves statistical significance. If the p-value for the two-sided Fisher's exact test is less than 0.01 and the point estimate for ORR in the cabozantinib arm is higher than that in the placebo arm, the null hypothesis of no difference in ORR will be rejected and it will be inferred that ORR is superior in the cabozantinib arm compared with the placebo arm.

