### *Lesions with prior local treatment*

- Lesions situated in a previously irradiated area, or in an area subjected to other loco-regional therapy, are not considered measurable.

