# 1 ADMINISTRATIVE STRUCTURE AND VERSION HISTORY

This study is being conducted under the sponsorship of Exelixis, Inc. Statistical programming and analyses are being conducted under contract by PPD in conjunction with Exelixis, Inc.

This version of the Statistical Analysis Plan (SAP) is based on amendment 1.0 of the protocol dated 23, April 2014.

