# 4.8 Changes to Planned Analyses

Substantive changes to the analyses described in the protocol or in approved versions of this plan will be fully documented in a revised version of the plan approved by the Sponsor prior to unblinding the study to conduct the analyses.

Clarifications, minor corrections, and operational considerations necessary to accurately conduct the analyses that do not materially change the nature of the analysis will be documented in an addendum to this plan that will be also be approved by the Sponsor prior to unblinding the study to conduct the analyses.

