# 7.2.2 Objective Response Rate (ORR)

#### **7.2.2.1 Definition**

For each subject, best overall response (BOR) is defined as the best tumor assessment category as determined by the investigator per RECIST 1.1 that occurs prior to any of the censoring events defined for the primary analysis of PFS as described in section 7.2.1.1. Tumor assessment categories are ranked as: confirmed complete response (CR), confirmed partial response (PR), stable disease (SD), progressive disease (PD) and not evaluable (NE). To be classified as confirmed CR or confirmed PR, confirmation must have occurred on a subsequent visit that is  $\geq 28$  days after the response was first observed.

The ORR is defined as the proportion of subjects with a BOR of confirmed CR or confirmed PR.

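### Protocol and SAP name different primary populations for the ORR test at 0.01, and the SAP's best-response rule has no cut-off at first progression

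*SAP*

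**What the plan says.** **Population.** SAP 7.2.2.3 states: "The primary analysis of ORR will include all subjects in the ITT population". Protocol 9.3.2 states: "The primary analysis of ORR will be performed for those subjects who have measurable disease at baseline within the ITT population". It adds: "Subjects who do not have any post-randomization tumor assessments will be counted as non-responders". Both sections attach the same two-sided Fisher's exact test at 0.01, carried out only if OS is significant at an interim or the final analysis.

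**Best overall response (BOR).** SAP 7.2.2.1 takes the best investigator-assessed RECIST 1.1 category "that occurs prior to any of the censoring events defined for the primary analysis of PFS as described in section 7.2.1.1". For a confirmed CR or PR, "confirmation must have occurred on a subsequent visit that is" at least 28 days after the response was first seen. SAP 7.2.1.1 and Table 3 treat radiographic progression as a PFS event. Their censoring list covers new anticancer therapy, non-bone radiation or tumor surgery before an event; a gap of missed assessments; no post-baseline assessment; and no event by the last assessment.

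**Version control.** SAP section 1 states: "This version of the Statistical Analysis Plan (SAP) is based on amendment 1.0 of the protocol dated 23, April 2014". SAP 4.8 states: "Substantive changes to the analyses described in the protocol or in approved versions of this plan will be fully documented in a revised version". The SAP version history (Table 2) has no entry on the ORR population or the BOR rule.

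**The concern.** A formally tested endpoint needs one denominator and one definition of a responder, both fixed before unblinding. Here the denominator depends on which document is followed, and the responder definition permits a result that the SAP contradicts elsewhere. SAP 7.5.2 ends a response at the PFS progression date, so a subject whose first response came after progression would be a responder with a negative response duration. At stake are the reported ORR and, for a result near the boundary, the ORR decision at 0.01. The primary OS test is not affected.

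**Working it through.** **What there is to reproduce.** The documents give no assumed ORR, ORR power or share of subjects with measurable disease. The stated ORR inputs are the arm sizes (507 and 253, Protocol 9.9) and the secondary alpha split, 0.04 + 0.01 = 0.05, which is exact. Responder counts and measurable-disease shares below are assumptions.

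**(a) Can the two populations differ?** Yes.
- Measurable disease is not among the criteria in Protocol 4.2 and 4.3, and SAP 5.5 tabulates it as Yes/No.
- Protocol Appendix G says: "Lesions situated in a previously irradiated area, or in an area subjected to other loco-regional therapy, are not considered measurable". Prior locoregional therapy is therefore one route to having no target lesion.
- In the Appendix G overall-response table, a subject without target lesions can be a responder only through CR. Such subjects mainly enlarge the ITT denominator.

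**Size of the change in ORR.** If a fraction f lacks measurable disease and none of them respond, subset ORR = ITT ORR / (1 − f). From 5.0%: 0.05/0.95 = 5.3%, 0.05/0.90 = 5.6%, 0.05/0.85 = 5.9%.

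**Equal removal from both arms, 22 vs 2 responders (two-sided Fisher):**

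| Share measurable | Denominators | p |
|---|---|---|
| 100% (ITT) | 507 / 253 | 0.0072 |
| 95% | 482 / 240 | 0.0072 |
| 90% | 456 / 228 | 0.0071 |
| 85% | 431 / 215 | 0.0070 |

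**Unequal removal.** A flip to p ≥ 0.01 at 22 vs 2 needs the measurable share to be about 4 points higher on cabozantinib than on placebo. With SE = √[f(1 − f)(1/507 + 1/253)], the required gaps of 4.25, 3.75 and 4.0 points at f = 5%, 10% and 15% are 2.53, 1.62 and 1.46 SE. Allocating 38, 76 or 114 non-measurable non-responders at random between the arms (hypergeometric) gives:

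| Responders | f = 5% | f = 10% | f = 15% |
|---|---|---|---|
| 22 vs 2 | 1.2% | 7.8% | 11.4% |
| 23 vs 2 | 0.0% | 0.01% | 0.2% |
| 25 vs 2 | about 0 | about 0 | about 0 |

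These figures are conditional on a result already at the boundary. Without that condition, with true ITT ORRs of 4% or 5% against 0.5% or 1% and 20,000 simulated trials per scenario, the two populations disagreed about p < 0.01 in 0.7% to 2.7% of trials.

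**(b) Does anything close the BOR window at progression?** The rules, side by side:
- SAP 7.2.2.1 closes it at PFS censoring events; SAP 7.2.1.1 makes progression an event.
- SAP 7.2.1.1 censors for new therapy only when it starts before an event. After progression, new therapy is no longer a PFS censoring event, so it does not close the window either.
- Appendix G makes each time point response independent of earlier ones and leaves BOR to the statistical analysis.
- Post-progression scans will exist. Treatment may continue after progression (SAP 2.1), and Protocol Appendix A continues scans until the later of 8 weeks after progression and the decision to stop treatment.

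**Case 1: confirmation after progression.** Appendix G thresholds are −30% from baseline for PR, and +20% and at least +5 mm from nadir for PD.

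| Scan (days after randomization) | Sum, mm | Reading |
|---|---|---|
| Baseline | 100 | |
| W9 (56) | 60 | −40%: PR |
| W17 (112) | 73 | +21.7% and +13 mm from 60: PD |
| W25 (168) | 68 | −32% from baseline, +13.3% from nadir: PR |

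W25 is 112 days after W9, so SAP 7.2.2.1 read literally gives a confirmed PR. Its duration under SAP 7.5.2 is 112 − 56 + 1 = 57 days (57/30.4375 = 1.9 months), ending 56 days before the confirming scan. W25 is 8 weeks after progression, within the required scan schedule.

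**Case 2: first response after progression.** Sums are 100, 95 (W9), 121 (W17: +27.4% and +26 mm, PD), 69 (W25: −31%, PR) and 68 (W33: confirmed). W33 is 16 weeks after progression, so it requires continued study treatment. Duration is 112 − 168 + 1 = −55 days (−1.8 months).

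**What one reclassified subject does at the boundary (507 / 253):** 21 vs 2 gives p = 0.0117 and 22 vs 2 gives 0.0072; 24 vs 3 gives 0.0118 and 25 vs 3 gives 0.0077.

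**The case against.** **The population conflict may be version lag.** The SAP follows Amendment 1.0, which is not supplied. The supplied protocol is later: it has an Open-Label Phase with crossover, which the SAP does not. The SAP also agrees with itself, since sections 3.1, 7 and 7.2.2.3 all use ITT, so an analyst who follows it faces no ambiguity. This stands as an explanation. The silence of the version history shows only that no change is recorded; it does not show that SAP 4.8 was breached. The two texts now in force still conflict.

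**The decision impact of (a) is small.** This stands: a flip needs a borderline result and a chance imbalance between arms.

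**Part (b) rests on constructed sequences.** It is true that no frequency is available and that any exact test turns on one subject at its boundary. The duration analysis also runs only if ORR exceeds 10%. At 51/507 against 2 to 5 placebo responders the Fisher p is about 0.00002 or less, so a negative duration and a flipped decision would not occur together at such rates. The duration example therefore shows that the rules are inconsistent, not that the test is at risk.

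**New therapy closes the window anyway.** This fails after progression, because therapy censors only if it precedes an event.

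**RECIST 1.1 may imply a cut at progression.** Possibly, but neither the SAP nor the protocol's adapted Appendix G states one.

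**A protocol change needs IRB/EC submission (Protocol 13) at up to 200 sites.** This stands, and it affects how the fix is made.

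**Conclusion.** Both parts hold. The protocol and SAP name different primary populations for the same 0.01 test, and the SAP's BOR rule as written counts responses seen or confirmed after progression. The population conflict mainly moves the reported ORR: 5.0% becomes 5.3% to 5.9% if 5% to 15% lack measurable disease and none of them respond. It changes the decision in 0.7% to 2.7% of simulated trials under the assumed response rates. The progression gap is probably rare in practice and its frequency cannot be estimated from the documents, but it concerns who counts as a responder in a formal test. This should be corrected before unblinding; it does not threaten the trial's primary conclusion. Confidence in the textual conflict is high. Confidence in the sizes is moderate, because they rest on assumed responder counts and measurable-disease shares.

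**What to change.** 1. **One population.** Name a single primary ORR population and keep the other as supportive, using the measurable-disease flag in SAP 5.5. All ITT is acceptable, with subjects who have no post-randomization assessment classed as not evaluable and counted as non-responders.
2. **Best-response window.** Rewrite SAP 7.2.2.1 so that BOR uses adequate tumor assessments (ATAs) up to and including the earliest of:
   - first radiographic progression;
   - the last ATA on or before the start of systemic or liver-directed non-protocol therapy, non-bone radiation or tumor resection;
   - the last ATA before a gap that triggers PFS censoring;
   - the last ATA on or before data cutoff.

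   A CR or PR and its confirmation at least 28 days later must both be among these ATAs and must precede first progression. State that an ATA is not dropped because the subject is censored on its date; otherwise a strict reading of the current rule could lose a response confirmed at the last scan.
3. **Waterfall plots.** State whether the same progression cut applies in SAP 7.2.2.4, which has the same gap.

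**Cost.** Wording in SAP 7.2.2.1, 7.2.2.3 and 7.2.2.4 and one version-history line, with no new data. A documented SAP revision under section 4.8 can settle the matter now, and Protocol 9.3.2 can be aligned at its next amendment. The ITT ORR will be slightly lower than the measurable-disease ORR, and responses seen or confirmed only after progression will not count.

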### 7.2.2.4 Supportive Analyses

To provide a more detailed understanding of anti-tumor activity, the maximum tumor reduction since baseline in target lesions will be derived for those subjects who have baseline and at least one post-baseline measure. The maximum percent tumor reduction from baseline in target lesions for each arm will be displayed graphically using waterfall

plots. For each subject, data from time points after the first date of any of the censoring events defined for the primary analysis of PFS as described in section 7.2.1.1. will be excluded from the waterfall plots.

## 7.3 Control of Type I Error

The multiplicity issue resulting from analysis of one primary endpoint (OS), two secondary efficacy endpoints (PFS and ORR), and planning two interim analyses for testing OS will be addressed by employing a fixed-sequence testing procedure, applying a modified Bonferroni procedure (dividing the alpha between the secondary endpoints), and implementing an alpha-spending function.

Up to three event-driven analyses of OS are planned: two interim analyses and a final analysis (see details in section 7.1.3). Inflation of Type 1 error associated with interim analyses will be controlled using a Lan-DeMets O'Brien-Fleming alpha-spending function.

Interim analysis of PFS and ORR are not planned. The testing of these two secondary endpoints will occur only if the result of either an interim analysis or the final analysis of OS achieves statistical significance. The hypothesis for PFS and ORR will be tested in parallel. PFS will be tested at the 2-sided  $\alpha$ =0.04 level of significance and ORR will be tested at the 2-sided  $\alpha$ =0.01 level of significance.

All other statistical evaluations of efficacy will be considered exploratory.

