## STATISTICAL METHODS

---

The primary efficacy analysis in this study is the comparison of overall survival (OS) in subjects treated with cabozantinib versus placebo.

For the primary endpoint, OS is defined as the time from randomization to death due to any cause. The final analysis of OS is event-driven and will be conducted after at least 621 deaths have been observed.

Progression-free survival (PFS) and objective response rate (ORR) are the secondary endpoints. PFS is defined as the time from randomization to the earlier of either disease progression per RECIST 1.1 as determined by the investigator or death from any cause. ORR is defined as the proportion of subjects experiencing a confirmed complete response (CR) or confirmed partial response (PR) per RECIST 1.1. Inflation of Type I error associated with testing multiple endpoints will be controlled by employing a fixed-sequence testing procedure and a modified Bonferroni procedure (dividing the alpha between the secondary endpoints: 0.04 for PFS, and 0.01 for ORR). The testing of the secondary endpoints (PFS and ORR) will occur only if the result of either an interim analysis or the final analysis of OS achieves statistical significance.

Up to three event-driven analyses of OS are planned: two interim analyses and a final analysis when 311, 466 and 621 deaths (ie, 50%, 75% and 100% information) have been observed respectively. Inflation of Type I error associated with interim analyses will be controlled using a Lan-DeMets O'Brien-Fleming alpha-spending function. Interim analysis of PFS and ORR are not planned.

OS and PFS will be summarized descriptively using the Kaplan-Meier method. Inferential comparisons between treatment arms will use the stratified log-rank test. The hazard ratio (HR) will be estimated using a stratified Cox proportional hazards model. Stratification will be based on the stratification factors used for the randomization. The ORR and 95% confidence intervals (CIs) will be provided. Inferential comparisons between treatment arms will use the Fisher's exact test.

For OS, a total of 621 deaths planned with two interim analyses (at 50% and 75% information) and a final analysis provides the study with 90% power for a 2-sided log-rank test with a 5% level of significance to detect a 31.6% increase in OS (HR = 0.76). Assuming an 8.2 month median OS in the placebo arm and exponential distribution of

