# 2.4 Power and Sample Size Justification

For the primary OS endpoint, up to three event-driven analyses are planned at 50%, 75%, and 100% information fraction (311, 466, and 621 deaths, respectively). A sample size of 760 subjects with a total of 621 events (and two interim analyses) provides the study with 90% power for a 2-sided log-rank test at 5% level of significance to detect a 31.6% increase in OS (HR = 0.76). Assuming a median OS of 8.2 months in the placebo arm (based upon the BRISK trial; Llovet 2012) and exponential distribution, this corresponds to median OS of 10.8 months in the cabozantinib arm.

In the current design, the minimum observed effect that would result in statistical significance for OS at the two interim and final analyses are 42.1% improvement (HR = 0.70, from 8.2 to 11.7 months), 25.7% improvement (HR = 0.80, from 8.2 to 10.3 months) and 18.4% improvement (HR = 0.84, from 8.2 to 9.7 months), respectively.

With an average accrual rate of 31.5 subjects per month and using a 2:1 treatment allocation ratio, an approximate total of 760 subjects (507 subjects in cabozantinib arm and 253 subjects in placebo arm) are required to observe the minimum number of events within the planned study duration (25 months accrual and approximately 38 months to observe the required events for OS). Currently since the average accrual rate is less than 31.5 subjects per month this will also prolong the study duration and time required to observe the required events for OS.

Power and sample size estimates were calculated using EAST v5 by Cytel Software.

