## 7.1.3 Primary Analysis

The primary analysis of OS will include all subjects in the ITT population.

The hypothesis testing between the two treatment arms will be performed using the stratified log-rank test with a 2-sided  $\alpha$ =0.05 level of significance. The stratification factors are as described in Section 2.5 and the values used for analysis will be those recorded in the (IxRS).

The median duration of OS and the associated 95% confidence interval (CI) for each treatment arm will be estimated using the Kaplan-Meier method. The stratified hazard ratio (HR) and its 95% CI will be estimated using a Cox proportional-hazard model with treatment group as the independent variable and stratified by the same randomization stratification factors as were used for the log-rank test.

The analysis of OS is event-based. Up to three analyses of OS are planned: two interim analyses and a final analysis that will occur when 311, 466 and 621 deaths (i.e. 50%, 75% and 100% deaths) have been observed respectively. Inflation of Type I error associated with interim analyses will be controlled using a Lan-DeMets O'Brien-Fleming alpha-spending function. The critical p-values (and observed HR) for rejecting the null hypothesis will be  $0.0031~(HR \le 0.70)$ ,  $0.0183~(HR \le .80)$  and  $0.044~(HR \le .84)$  at the time when 311, 466 and 621 deaths (50%, 75% and 100% information) are observed respectively. The actual critical values will depend upon the true number of events observed at each analysis. The interim analyses of OS are also described in section 7.4.

At an analysis time point, if the p-value for the stratified log-rank test is less than the critical value for rejecting the null hypothesis and the HR is < 1, the null hypothesis will be rejected

and it will be inferred that OS is superior in the cabozantinib arm compared to the placebo arm.

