## 7.4 Interim Analyses

The size of the trial is based upon the assumptions currently available and provides high power to detect what the Sponsor believes is the smallest clinically meaningful difference in OS under these assumptions. However, as there is uncertainty in the assumptions, interim analyses provides an opportunity to stop the trial early if the treatment benefit of cabozantinib is larger than expected, potentially allowing cabozantinib to become available sooner to this patient population.

Two interim analyses for primary endpoint of OS are planned. The interim analyses will be conducted at the time when approximately 311 and 466 deaths have been observed respectively. It is anticipated that this will be at approximately the 50% and 75% information fraction respectively for OS. Type I error for the interim analysis will be controlled by a Lan-DeMets O'Brien-Fleming alpha spending function as described in

Section 7.3. The actual critical values employed at the interim and final analyses of OS will depend upon the actual information fraction at the time of the interim analyses.

If the planned first or second interim OS analysis achieves overwhelming evidence of efficacy (p-value = 0.0031 or 0.0183, respectively, under trial design assumptions) in favor of cabozantinib, analyses of the secondary endpoints will be performed as planned. Interim analyses will be evaluated by the IDMC. Monitoring guidance will be provided to allow the study to be stopped early if the null hypothesis for OS is rejected in favor of cabozantinib. A nonbinding boundary for harm will be used by the IDMC to help evaluate subject safety. Stopping for futility is not planned.

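### PFS and ORR are tested at fixed 0.04 and 0.01 at whichever OS look first crosses, so strong control of false superiority claims is not guaranteed, although the excess is small

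*SAP*

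**What the plan says.** OS is the primary endpoint. SAP 7.1.3: "The hypothesis testing between the two treatment arms will be performed using the stratified log-rank test with a 2-sided" level of 0.05. Three looks are planned at "50%, 75%, and 100% information fraction (311, 466, and 621 deaths, respectively"). A Lan-DeMets O'Brien-Fleming spending function gives critical p-values of 0.0031, 0.0183 and 0.044 (SAP 7.1.3, protocol 9.2.2).

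For the secondary endpoints, SAP 7.3 and protocol 9.4 say that testing "will occur only if the result of either an interim analysis or the final analysis of OS achieves statistical significance". PFS and ORR are then tested in parallel. PFS superiority needs a 2-sided p below 0.04 and a hazard ratio below 1 (SAP 7.2.1.3). ORR superiority needs a 2-sided Fisher p below 0.01 and a higher rate on cabozantinib (SAP 7.2.2.3). Neither threshold depends on the look. If OS crosses at an interim, "analyses of the secondary endpoints will be performed as planned" (SAP 7.4; protocol 9.8 agrees). No event count, cutoff or information fraction is set for PFS or ORR, and no interim analysis of either is planned.

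The protocol synopsis makes the claim of control: "Inflation of Type I error associated with testing multiple endpoints will be controlled by employing a fixed-sequence testing procedure", together with the 0.04/0.01 split.

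**The concern.** A fixed sequence that passes the full level to the next hypothesis is valid when everything is analysed at one time. Here the OS result chooses the time. OS and PFS are measured on the same subjects and share deaths as events, so a look where OS happens to run high is more often one where PFS does too. The spending function corrects OS for this choice of look. Nothing corrects PFS or ORR.

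The error at stake is a false superiority claim on a secondary endpoint when OS truly benefits and that endpoint does not. Superiority requires the favourable direction, so the implied one-sided allotments are 0.04/2 = 0.020 for PFS, 0.01/2 = 0.005 for ORR and 0.025 together.

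**Working it through.** **Reproducing the plan's figures.** Lan-DeMets O'Brien-Fleming spending of one-sided 0.025 at fractions 0.5, 0.75 and 1 gives z-bounds 2.963, 2.359 and 2.014. The two-sided p-values are 0.00305, 0.01833 and 0.04398, which match the plan. SAP 2.4 says 621 deaths "provides the study with 90% power for a 2-sided log-rank test at 5% level of significance" "to detect a 31.6% increase in OS (HR = 0.76"). With 2:1 allocation the Schoenfeld formula gives (1.960 + 1.282)² / [(2/9)(ln 0.76)²] ≈ 628 deaths, close to 621. Fixed-sample power at 621 deaths is 89.7%. The design drift is |ln 0.76| × √(621 × 2/9) = 3.22.

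**When the secondaries would be tested.** At HR 0.76, OS first crosses at the three looks with probability 25%, 42% and 22%. An interim is therefore the likely time.

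**Model.** The OS and PFS statistics are jointly normal over the three looks. OS has a true benefit and PFS is null. PFS is tested once, at the first OS crossing:

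rate = Σₖ P(OS first crosses at look k and Z_PFS,k > 2.054), where 2.054 is the one-sided 0.020 critical value.

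If OS is null, the rate cannot exceed the 0.025 chance that the gate opens in favour of cabozantinib. If the OS effect is so large that OS always crosses at the first look, PFS is in effect tested at one time and the rate returns to 0.020. The excess lies between these cases. The table takes the largest value over the OS effect. The documents give no correlations, so these are assumed. The 0.60/0.84/1 fractions assume a PFS median of 5.2 months (the Phase 2 figure in protocol 1.3.3.3.2) and 31.5 subjects per month.

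| OS-PFS correlation | One-sided PFS rate, same fractions as OS | One-sided PFS rate, PFS fractions 0.60/0.84/1 | PFS rejections in either direction, same fractions |
|---|---|---|---|
| 0.3 | 0.0213 | 0.0212 | 0.0390 |
| 0.5 | 0.0225 | 0.0223 | 0.0372 |
| 0.7 | 0.0243 | 0.0240 | 0.0355 |
| 0.9 | 0.0272 | 0.0266 | 0.0339 |
| Allotted | 0.020 | 0.020 | 0.040 |

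At the design drift of 3.22 the one-sided rate is about 0.021 to 0.0225: about 0.022 at correlation 0.5 and 0.0212 at 0.9.

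**Patient-level check.** Log-rank tests were simulated in 25,000 trials per scenario, with PFS null and longer post-progression survival on cabozantinib. Assumed PFS medians of 2, 3 and 5.2 months gave correlations of 0.29, 0.41 and 0.67 and one-sided PFS rates of 0.0226, 0.0248 and 0.0229 (standard error about 0.001).

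**ORR.** With a normal statistic the one-sided rate would be 0.0054 to 0.0063 against 0.005 for OS-ORR correlations of 0.3 to 0.7. The plan uses Fisher's exact test, which is conservative when responses are rare; Phase 2 had 2 confirmed responses in 41 (5%). With 507 and 253 subjects and an assumed common response rate of 1%, 2%, 3% or 5%, its one-sided size is 0.0002, 0.0023, 0.0029 or 0.0036. The inflation factor at correlation 0.7 is 0.0063/0.005 = 1.26, and 0.0036 × 1.26 = 0.0045, still below 0.005. A factor of 1.44, from a more extreme correlation, gives 0.0036 × 1.44 = 0.0052.

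**Both secondaries at the design effect, correlation 0.5.** With an ORR factor of 1.12, 0.0036 × 1.12 = 0.0040. The sum 0.022 + 0.0040 ≈ 0.026 is an upper bound on the chance of either false claim, against 0.025.

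**The case against.** The strongest reply is that the plan states its levels as 2-sided, and on that scale nothing is exceeded. Counting rejections in either direction, PFS stays at or below 0.040 and PFS with ORR at or below 0.048. That is correct. But the total stays low because selecting on a favourable OS result empties the unfavourable tail. The only claim the plan makes is superiority, and SAP 7.2.2.2 states the ORR null as one-sided. The favourable tail is the one that matters, and it is the one that grows.

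A reader might double the one-sided rates at the design effect and add them, 0.0446 + 0.0112 = 0.056, and conclude that the stated 0.05 is breached. The documents do not support this. The sum compares doubled one-sided rates with a 2-sided level, adds two marginal rates as if they were a joint one, and treats ORR as normal when Fisher's test is specified.

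A reader might also infer that PFS may be tried at 0.04 at each look. The text does not provide for that: no interim analyses of PFS or ORR are planned, which reads as one test each. The plan does not, however, expressly exclude re-testing a secondary that fails at an interim crossing. With re-testing the one-sided PFS rate would be 0.031 to 0.040.

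It is also fair that the upper figures in the table are maxima over the OS effect, and that an OS benefit with exactly no PFS effect is a special case. Strong control has to cover that case, but it does limit the practical weight of the point.

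**Conclusion.** The concern holds in a limited form. The gate and the 0.04/0.01 split do not by themselves guarantee the error control that the documents claim, because the secondary thresholds ignore the look at which they are applied. For PFS the one-sided rate of false superiority is about 0.021 to 0.025 against 0.020 for correlations of 0.3 to 0.7, up to about 0.027 at 0.9. For ORR any excess is largely absorbed by Fisher's test at low response rates.

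It would be too strong to say that error control fails in general. If OS is null, the gate caps false claims at 0.025, and with one test per endpoint the excess is small. The sizes rest on assumed correlations, a normal approximation for PFS, and one test per secondary. The gap itself follows from the wording alone.

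**What to change.** In SAP 7.2.1.3, 7.2.2.3, 7.3 and 7.4, and in the synopsis and sections 9.3, 9.4 and 9.8 of the protocol:

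- Give PFS (0.04) and ORR (0.01) their own group-sequential boundaries over the three OS looks, using each endpoint's own information fraction at that look. This requires a planned final information level for each endpoint, which the documents do not now give.
- Test each secondary once, at the look where OS crosses, against its boundary for that look.
- State that a secondary that fails is not re-tested at the full level.

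With O'Brien-Fleming-type spending and fractions 0.5/0.75/1, the 2-sided PFS levels are 0.0020, 0.0138 and 0.0355, and the ORR levels 0.0001, 0.0023 and 0.0092. The one-sided false-superiority rates are then at most 0.0186 for PFS and 0.0026 for ORR, within 0.020 and 0.005. If PFS information is further along, for example 0.7/0.9/1, the PFS levels are about 0.011, 0.025 and 0.031, so the early levels are less strict.

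The cost is wording plus a stricter nominal level if OS crosses at an interim. A lighter alternative is to fix one analysis time per secondary in advance, independent of the OS result; the cost there is that an interim OS success may have to wait for the secondary tests. Under SAP 4.8 a substantive change of this kind belongs in a revised SAP approved before unblinding.
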